7.4.5.3 Duration of Complete Remission

The duration of complete remission (DOCR) is defined as the duration from the date of first documented evidence of CR to the date of documented relapse of disease or disease progression, as determined by the investigator per the modified IWG MDS criteria (Cheson 2006), or death due to any cause, whichever occurs first.

DOCR will be calculated for participants with CR achieved by Cycle 7 Day 1.

The following analyses will be conducted separately:

- [1] Primary analysis of DOCR estimand (investigator response in mITT analysis set)
- [2] Sensitivity analysis of DOCR estimand (investigator response in ITT analysis set)

DOCR will be estimated using Kaplan-Meier product-limit estimates. The median estimate of DOCR and corresponding 95% CIs based on the method of Brookmeyer and Crowley (Brookmeyer 1982) will be provided for each treatment group. The median follow-up time of DOCR and its corresponding 95% CI will be calculated using the reverse Kaplan-Meier approach (Sathish 2019). The analysis will only be for participants who are CR responders. Event and censoring rules for DOCR are provided in Table 13. A sensitivity analysis of the DOCR will also be performed using the alternative censoring rule identified in situation number 6 by using both mITT and ITT analysis sets.

Table 13 Assignments for Event and Censoring Dates for DOCR Analysis

Situation Number	Situation (Occurring on or After First Date of CR Response)	Date of Event or Censoring	Outcome
1	No post-baseline response assessments after the first CR and the participant has	First date of CR response	Censored

Situation Number	Situation (Occurring on or After First Date of CR Response)	Date of Event or Censoring	Outcome
	not died or developed disease progression/relapse (if the participant has died or developed disease progression /relapse then follow the rules indicated in situations 7 and 8)		
2	Disease progression/relapse documented at scheduled visits within extended loss- to-follow-up time ^[1]	Date of assessment of disease progression/relapse	Event
3	Disease progression/relapse documented between scheduled (unscheduled) visits within extended loss- to-follow-up time ^[1]	Date of assessment of disease progression/relapse	Event
4	No disease progression/relapse (or death)	Date of last adequate response assessment ^[2]	Censored
5	New anticancer therapy other than HSCT started prior to documented disease progression/relapse or death	Date of last adequate response assessment prior to start of new anticancer therapy other than HSCT	Censored
6	HSCT started prior to documented disease progression/relapse or death	Date of last adequate response assessment occurring prior to documented disease progression/relapse or death, irrespective of HSCT date ^[2] Date of assessment of disease progression/relapse or death ^[SA]	Censored Event
7	Death without an extended loss-to-follow-up time ^[1]	Date of death	Event
8	Death or developed disease progression/relapse after an extended loss-to-follow-up time (≥2 missed consecutive assessment) ^[1]	Date of last adequate response assessment ^[2] prior to the ≥2 missed consecutive assessments	Censored

Abbreviations: CR = complete remission; HSCT = hematopoietic stem cell transplantation

^[SA] Alternative rule for handling of events for DOCR.

^[1] Extended loss-to-follow-up time is defined as the last non-missing adequate response assessment and event (death or disease progression/relapse). Extended loss-to-follow-up time is 208 days. This cutoff is calculated based on the protocol scheduled procedure: the 28-day treatment cycle has ± 3 days window, response assessment is expected to be conducted every 3 months (with ± 14 days window). Thus, 2 consecutive scheduled assessments window is $2 \times [(30 \times 3 + 14] = 208$ days. Within extended loss-to-follow-up time is defined as ≥ 208 days; after an extended loss-to-follow-up time is defined as ≥ 208 days.

^[2] An adequate assessment is defined as an assessment where the Investigator performed all the procedures required for assessment and documented the outcome.

7.4.5.4 Duration of Overall Response

The duration of overall response is defined as the duration from the date of first documented evidence of CR, PR, mCR, or HI, to the date of documented disease progression or relapse of disease as determined by the investigator per the modified IWG MDS criteria (Cheson 2006), or death due to any cause, whichever occurs first.

The following analyses will be conducted separately:

- [1] Primary analysis of duration of overall response estimand (investigator response in mITT analysis set)
- [2] Sensitivity analysis of duration of overall response estimand (investigator response in ITT analysis set)

The duration of overall response will be estimated using Kaplan-Meier product-limit estimates. The median estimate of duration of overall response and corresponding 95% CIs based on the method of Brookmeyer and Crowley (Brookmeyer 1982) will be provided for each treatment group. The median follow-up time of duration of overall response and corresponding 95% CI will be calculated using reverse Kaplan-Meier approach (Sathish 2019). The analysis will only be for participants who are overall responders. Event and censoring rules for duration of overall response are provided in Table 14. A sensitivity analysis of the duration of overall response will also be performed using the alternative censoring rule identified in situation number 6 in both mITT and ITT analysis sets.

Table 14Assignments for Event and Censoring Dates for Duration of Overall
Response Analysis

Situation Number	Situation (Occurring on or After First Date of Response)	Date of Event or Censoring	Outcome
1	No post-baseline response assessments after the first response and the participant has	First date of overall response	Censored

Situation Number	Situation (Occurring on or After First Date of Response)	Date of Event or Censoring	Outcome
	not died or developed disease progression/relapse (if the participant has died or developed disease progression/relapse then follow the rules indicated in situations 7 and 8)		
2	Disease progression/relapse documented at scheduled visits within extended loss-to-follow- up time ^[1]	Date of assessment of disease progression/relapse	Event
3	Disease progression/relapse documented between scheduled (unscheduled) visits within extended loss-to-follow-up time ^[1]	Date of assessment of disease progression/relapse	Event
4	No disease progression/relapse (or death)	Date of last adequate response assessment ^[2]	Censored
5	New anticancer therapy other than HSCT started prior to documented disease progression/relapse or death	Date of last adequate response assessment prior to start of new anticancer therapy	Censored
6	HSCT (prior to documented disease progression/relapse or death)	Date of last adequate response assessment occurring prior to documented disease progression/relapse or death, irrespective of HSCT date ^[2]	Censored
		Date of assessment of disease progression/relapse or death ^[SA]	Event
7	Death without extended loss-to- follow-up time ^[1]	Date of death	Event
8	Death or disease progression/relapse after an extended loss-to-follow-up time (≥2 missed consecutive assessment) ^[1]	Date of last adequate response assessment ^[2] prior to the \geq 2 missed consecutive assessments	Censored

Abbreviations: CR = complete remission; HSCT = hematopoietic stem cell transplantation

^[SA] Alternative rule for handling of events for duration of Overall Response.

^[1] Extended loss-to-follow-up time is defined as the last non-missing adequate response assessment and event (death or disease progression/relapse). Extended loss-to-follow-up time is 208 days. This cutoff is calculated based on the protocol scheduled procedure: the 28-day treatment cycle has \pm 3 days window, response assessment is expected to be conducted every 3 months (with \pm 14 days window). Thus, 2 consecutive scheduled assessments window is $2 \times [(30) \times 3 + 14] = 208$ days. Within extended loss-to-follow-up time is defined as >208 days; after an extended loss-to-follow-up time is defined as >208 days.

^[2] An adequate assessment is defined as an assessment where the Investigator performed all the procedures required for assessment and documented the outcome.

The duration of CR/PR will also be summarized. It is defined as the duration from the date of first documented evidence of CR or PR to the date of documented relapse of disease or disease progression, as determined by the investigator per the modified IWG MDS criteria (Cheson 2006), or death due to any cause, whichever occurs first. Duration of CR/PR will be estimated using Kaplan-Meier product-limit estimates. The median estimate of duration of CR/PR and corresponding 95% CIs based on the method of Brookmeyer and Crowley (Brookmeyer 1982) will be provided for each treatment group. The analysis will only be for participants who are CR/PR responders. Event and censoring rules for duration of CR/PR are provided in Table 13.

7.4.5.5 *Time to CR*

Time to CR is defined as the duration from the date of randomization to the date of the first documented evidence of CR as determined by the investigator per the modified IWG MDS criteria (Cheson 2006).

Time to CR will be calculated for participants with CR achieved by Cycle 7 Day 1.

The following analyses will be conducted separately:

- [1] Primary analysis of time to CR estimand (investigator response in mITT analysis set)
- [2] Sensitivity analysis of time to CR estimand (investigator response in ITT analysis set)

Time to CR will be summarized using descriptive statistics by treatment group and only for participants who are responders from the mITT analysis set.

Time to CR will be summarized using descriptive statistics by treatment group and only for participants who are responders from the ITT analysis set for the sensitivity analysis.

7.4.5.6 *Time to Initial Response*

Time to initial response is defined as the duration from the date of randomization to the date of the first documented evidence of CR, PR, mCR, or HI as determined by the investigator per the modified IWG MDS criteria (Cheson 2006).

The following analyses will be conducted separately:

- [1] Primary analysis of time to initial response estimand (investigator response in mITT analysis set)
- [2] Sensitivity analysis of time to initial response estimand (investigator response in ITT analysis set)

Time to initial response will be summarized using descriptive statistics by treatment group and only for participants who are responders from the mITT analysis set.

Time to initial response will be summarized using descriptive statistics by treatment group and only for participants who are responders from the ITT analysis set for the sensitivity analysis.

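### SAP Tables 13 and 14 define 'within' and 'after' extended loss to follow-up by the same inequality, so the 208-day rule for progression/relapse misassigns events as written

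*SAP*

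**What the plan says.** SAP 7.4.5.3 (Table 13) and 7.4.5.4 (Table 14) give the event and censoring rules for duration of complete remission (DOCR) and duration of overall response. Duration of CR/PR also uses Table 13.

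- Rows 2 and 3, outcome Event. In Table 14 these read "Disease progression/relapse documented at scheduled visits within extended loss-to-follow- up time" and "Disease progression/relapse documented between scheduled (unscheduled) visits within extended loss-to-follow-up time".
- Row 8, outcome Censored: death or progression/relapse "after an extended loss-to-follow-up time (≥2 missed consecutive assessment"), dated to the last adequate assessment before the missed ones.
- Row 7, outcome Event. In Table 13 this is "Death without an extended loss-to-follow-up time", dated to death.

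Footnote [1] supplies the threshold: "Extended loss-to-follow-up time is 208 days", derived from a schedule in which "response assessment is expected to be conducted every 3 months" with a 14-day window. It then defines the two terms. Table 14 says "Within extended loss-to-follow-up time is defined as >208 days; after an extended loss-to-follow-up time is defined as >208 days". Table 13 says "Within extended loss-to-follow-up time is defined as ≥ 208 days; after an extended loss-to-follow-up time is defined as ≥ 208 days". Footnote [2] of Table 15 (event-free survival, SAP 7.4.5.7) repeats the Table 14 wording.

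**The concern.** 'Within' and 'after' lead to opposite outcomes, so their definitions should be complementary. They are identical in each footnote. Every progression or relapse that reaches rows 2, 3 or 8 of Tables 13 and 14 is assigned by this threshold. A program written to the footnote would find no row for the ordinary relapse and two contradictory rows for a late one. Someone would then have to choose a rule that the SAP does not state, although SAP section 4 gives avoiding post hoc decisions as its purpose. DOCR also matters to readers because it describes how durable the primary-endpoint responses are.

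**Working it through.** **Inputs.** Assessment interval 3 months, taken as 30 × 3 = 90 days; window ±14 days; cutoff 208 days; the two inequality pairs (all from footnote [1] of Tables 13 and 14). Row outcomes are from the same tables.

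**Step 1: the plan's own figure.** 2 × (30 × 3 + 14) = 2 × 104 = 208 days. It reproduces exactly.

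**Step 2: when an ordinary relapse is found.** With no missed visit, the nominal gap from the last assessment is 90 days. It is 90 + 14 = 104 if only the second visit is late, and 90 + 14 + 14 = 118 if the first visit was early and the second late. On treatment, a delayed cycle start (protocol 6.5.1) can lengthen the gap, so 118 is not a strict maximum. All these values are well below 208.

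**Step 3: apply the footnotes literally to progression/relapse.** Gap = days from last adequate assessment to event.

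| Gap | Table 13 (≥208 / ≥208) | Table 14 (>208 / >208) |
|---|---|---|
| 90 | neither row | neither row |
| 118 | neither row | neither row |
| 207 | neither row | neither row |
| 208 | event and censored | neither row |
| 209 | event and censored | event and censored |
| 300 | event and censored | event and censored |

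No gap receives exactly one outcome.

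**Step 4: deaths and EFS.** Row 7 of Tables 13 and 14 uses 'without', and row 8 uses 'after'. In Table 15 the event rows 3, 4 and 7 use 'without', the censoring rows 8 and 9 use 'after', and no row uses 'within'. Reading 'without' as 'not after' gives one outcome per gap: event up to 207 days in Table 13 and up to 208 days in Tables 14 and 15, censored beyond. The only residue is day 208 itself, where a death is censored under Table 13 and an event under Tables 14 and 15.

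**Step 5: the missed-assessment wording against 208 days.** Assume the last assessment was on schedule. On treatment, with assessments every three 28-day cycles and a ±3-day window, two have been missed by about 2 × 3 × 28 + 3 = 171 days. In Disease Follow-up, two have been missed by about 2 × 90 + 14 = 194 days. An unscheduled relapse at day 200 therefore follows two missed assessments but lies inside 208 days. The two descriptions are close without being the same rule.

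**Step 6: complementary definitions.** With ≤208 for within and >208 for after, gaps of 90, 118, 207 and 208 days are events, and 209 and 300 are censored: one outcome each. With <208 and ≥208, only day 208 changes.

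**The case against.** The strongest reply is that nobody would program it this way. Row 8 carries its own description, two or more consecutive missed assessments, and 208 days is derived as two assessment windows. A relapse found at the next visit has no missed assessment and cannot belong in row 8. This stands as to direction: a short gap is meant to be an event and a long gap a censoring. A reader might infer from the duplicated inequality that the rule cannot distinguish events from censorings at all; the documents do not support that. The context does not settle day 208, or cases such as day 200 in Step 5.

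A reader might also infer that EFS is affected in the same way, because Table 15 repeats the footnote. It is not. No Table 15 row uses 'within', so that definition is stray and the split on 'without' versus 'after' still works. The same holds for deaths in Tables 13 and 14.

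A second reply is that a ≤ sign was misread when the PDF was converted to text. This cannot be excluded: the near-identical footnotes show different signs, and nearby text is damaged. It does not readily explain the same duplication in three separate footnotes, but the source PDF should be checked first.

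Third, the consequence is limited. DOCR and duration of overall response are summarized by Kaplan-Meier estimates, no between-arm test is specified for them, and they lie outside the alpha hierarchy, which covers only CR and OS (SAP 7.1.1). That stands and bounds the importance.

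**Conclusion.** The point holds for progression/relapse in DOCR, duration of CR/PR and duration of overall response. As written, the threshold assigns a gap beyond 208 days to both outcomes and an ordinary gap of about 90 to 118 days to neither. It is a wrong threshold in a rule whose intent can be recovered. For deaths and EFS, what remains is a stray definition, an unstated meaning of 'without', and a boundary sign in Table 13 that differs from Tables 14 and 15. The primary CR analysis and OS (Table 12) are unaffected. The number of participants concerned cannot be given from the documents.

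The conclusion assumes that the signs in the source PDF match the text read here and that the clock runs from the last adequate assessment to the event. It is worth correcting because the rule governs how durability of response is reported and the correction is very cheap.

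**What to change.** First confirm the signs against the source PDF. Then:

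1. In footnote [1] of Tables 13 and 14 and footnote [2] of Table 15, define within (or without) as 208 days or less from the last adequate assessment to the event, and after as more than 208 days. Use the same sign in all three tables.
2. State that the 208-day rule is how two or more missed consecutive assessments is applied, so that a case such as day 200 has one answer.
3. State that the rule decides between the event rows and the 'after' censoring rows (row 8 in Tables 13 and 14; rows 8 and 9 in Table 15) only when no other censoring row already applies, such as those for new anticancer therapy or HSCT. Without this, a relapse 100 days after the last assessment but following new anticancer therapy would appear to be an event, although row 5 of Tables 13 and 14 censors it.

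The cost is a corrected inequality in three footnotes and two added sentences. No new data are needed and the design does not change. The correction should be made before unblinding.

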7.4.5.7 Event-Free Survival

EFS is defined as the time from the date of randomization to the date of transformation to AML or death due to any cause, whichever occurs first.

EFS analyses will be based on the ITT analysis set at the time of OS analysis.

EFS will be estimated using Kaplan-Meier product-limit estimates and will be presented for each treatment group and only for participants who have an event or who are censored in the ITT analysis set. Event and censoring rules for EFS are provided in Table 15.

A log-rank test stratified by IPSS-R risk group (Intermediate, High, and Very High Risk) and by geographical region (North America, Western Europe, plus Israel, and Eastern Europe) will be used to analyze the difference in EFS between treatment groups at 2-sided 5% significance level.

The number and percentage of participants with an event or who were censored will be summarized by treatment group. The 25th percentile, median, and 75th percentile EFS (along with corresponding 95% CIs) will also be presented. Landmark analyses (EFS rates, 95% CI, and number of participants at risk) will occur at 6 and 12 months post first dose and will be analyzed using the Kaplan-Meier method. The CIs will be calculated using the method of Brookmeyer and Crowley (Brookmeyer 1982).

Additionally, a separate summary of reasons for censoring, plots of the Kaplan-Meier estimates, a by-participant listing of the derived efficacy data used for the EFS analysis, and a listing of reasons for censoring will be provided.

Sensitivity Analysis 1: EFS analysis using alternative censoring rules.

A sensitivity analysis of EFS will also be performed using the alternative censoring rules identified in situation numbers 4, 7, and 9 in Table 15.

Sensitivity Analysis 2: Violation of proportional hazard assumption.

If the proportional hazard assumption does not hold for the EFS analysis, the RMST may be substituted as appropriate. RMST is the participant's life expectancy until time t and can be estimated nonparametrically by the area under the Kaplan-Meier curve up to time t (Tian 2020). Time t will be chosen at the 90th percentile of observed follow-up times (Tian 2020).

The estimated RMST difference in EFS between treatment groups will be reported with 95% CIs. The SAS procedure RMSTREG will be used with a linear link function.

Table 15Assignments for Primary and Alternative Event and Censoring Dates
for EFS Analysis

Situatio	Situation	Date of Event or Censoring	Outcome

^[2] Extended loss-to-follow-up time is defined as the last non-missing adequate response assessment and event (death or disease progression/failure/relapse). Extended loss-to-follow-up time is 208 days. This cutoff is calculated based on the protocol scheduled procedure: the 28-day treatment cycle has \pm 3 days window, response assessment is expected to be conducted every 3 months (with \pm 14 days window). Thus, 2 consecutive scheduled assessments window is $2 \times [30 \times 3 + 14] = 208$ days. Within extended loss-to-follow-up time is defined as >208 days; after an extended loss-to-follow-up time is defined as >208 days.

^[3] An adequate assessment is defined as an assessment where the Investigator performed all the procedures required for assessment and documented the outcome.

Transformation to AML

Since EFS will be analyzed at the time of the final OS analysis, transformation to AML in the mITT Analysis Set will be analyzed at the time of the primary CR analysis. The number of participants who had disease transformation to AML will be summarized by treatment group, overall, and separately by two groups: those who achieved CR by Cycle 7 Day 1 and those who did not.

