6.4.1 Efficacy Endpoints

6.4.1.1 Primary Efficacy Endpoint and Estimand

The primary efficacy endpoint is CR defined as CR achieved by Cycle 7 Day 1, as determined by the investigator per the modified IWG MDS criteria (Cheson 2006). Peripheral blood counts to support the achievement of CR must be in the absence of transfusions or growth factors within the previous 7 days. The CR should be confirmed at least 4 weeks from the date of marrow sampling. Instructions for the assessment of IWG response including the provision of a 2-week window after the response assessment bone marrow aspiration for unscheduled hematology evaluations to meet the IWG criteria of CR are provided in the Study SY-1425-301 protocol, Section 8.1.1. The calculation of the rate of CR for each treatment group is:

CR rate (%) = number of *CR* responders achieved by Cycle 7 Day 1 / number of participants in the modified Intent-to-Treat (mITT) analysis set \times 100. The denominator is the mITT population in each treatment group.

Non-CR responders (mITT – CR responders) are participants who do not achieve CR or meet any of the following criteria:

Version 4.0

- 1. Do not have any post-baseline response assessments.
- 2. All response assessment results are missing or not done.
- 3. Discontinue prior to having a post-baseline assessment.
- 4. Withdraw consent before achieving a response.
- 5. Die before achieving a response.
- 6. Start a new anticancer therapy before achieving a response.
- 7. Experience prolonged treatment interruption requiring permanent withdrawal of study drug before achieving a response.

Table 3Primary Estimand

		Esti	mand Categ	ory	
		Population		Intercurrent	Populatio
		(Based on	Variable/	Event;	n Level
Objective	Treatment	mITT)	Endpoint	Strategy	Summary

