7.4.6.7 Transfusion Rate

Participants who have been on treatment for at least 56 days are considered evaluable for this analysis.

Definitions:

• Baseline Transfusion Dependence:

Transfusion of ≥ 1 unit of RBCs and/or platelets during the 56 days prior to date of randomization.

• Baseline TI:

No RBC or platelet transfusions during the 56 days prior to date of randomization.

• Post-baseline TI:

Post-baseline TI is defined as a period of at least 56 days with no RBC or platelet transfusion since the date of randomization to the last dose of study drug + 30 days, the initiation of post-treatment therapy, or death, whichever occurs first.

Analyses:

The mITT Analysis Set will be used for the following transfusion rate analyses.

Overall transfusion status (RBC or platelets), RBC transfusion status, and platelet transfusion status will be analyzed separately as below:

• Rate of conversion of baseline transfusion dependence to post-baseline TI in the baseline transfusion-dependent mITT participants.

The number and percentage of mITT participants who are transfusion dependent at baseline and the number and percentage of baseline transfusion-dependent mITT participants who achieved post-baseline TI, along with respective 95% exact binomial CIs, will be summarized by treatment group.

• Rate of maintenance of baseline TI in the baseline transfusion-independent mITT patients.

The number and percentage of mITT participants who are transfusion independent at baseline and the number and percentage of baseline transfusion-independent mITT participants who maintained TI post-baseline will be summarized by treatment group.

In addition, the median number of units of RBC and platelets received in 56 days blocks (e.g., Day 1 to Day 56, Day 57 to Day 112, and etc.) starting from Cycle 1 Day 1 will be reported for each treatment group.

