7.4.6.10 Exploratory Comparison of Response Categories and TI

The TI status (achieved TI versus did not achieve TI) of participants in the mITT Analysis Set will be summarized by treatment group for the following response categories: best overall response of CR by Cycle 7 Day 1, CR or PR, mCR with HI, mCR without HI, HI (in participants not achieving CR, PR, or mCR), and participants without a response.

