8.1.6 Exploratory Comparison of Response Categories and TI

Section 7.4.6.10 was added to detail an additional exploratory analysis examining the TI status of participants based on CR in order to determine association between the two.

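### The AML count split by CR at Cycle 7 Day 1 has no landmark and can show a CR difference where there is none; the TI-by-response table has a related at-risk problem (minor)

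*SAP*

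**What the plan says.** **AML.** SAP 7.4.5.7 defers EFS to the final OS analysis. In the meantime, "transformation to AML in the mITT Analysis Set will be analyzed at the time of the primary CR analysis". The output is a number of participants by treatment group, overall, and separately for "those who achieved CR by Cycle 7 Day 1 and those who did not". No test, time-to-event method or at-risk condition is given. The landmark analyses named earlier in that section are Kaplan-Meier EFS rates at 6 and 12 months; they do not condition on CR status.

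**CR status.** SAP 6.4.1.1 classes as non-CR anyone who dies, withdraws consent or starts new anticancer therapy before responding, or who has no post-baseline assessment. It adds "The CR should be confirmed at least 4 weeks from the date of marrow sampling" and "Peripheral blood counts to support the achievement of CR must be in the absence of transfusions or growth factors within the previous 7 days".

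**TI.** SAP 7.4.6.10 states "The TI status (achieved TI versus did not achieve TI) of participants in the mITT Analysis Set will be summarized by treatment group", across six response categories from CR by Cycle 7 Day 1 to no response. SAP 8.1.6 gives the purpose: "examining the TI status of participants based on CR in order to determine association between the two". SAP 7.4.6.7 defines TI as "a period of at least 56 days with no RBC or platelet transfusion since the date of randomization", with the window closing at last dose plus 30 days, post-treatment therapy or death. That section has its own entry rule, "Participants who have been on treatment for at least 56 days are considered evaluable for this analysis", which 7.4.6.10 does not repeat.

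**Stopping after Cycle 7 Day 1.** Protocol 7.1 ends study drug for participants without at least HI in one lineage once the Cycle 7 Day 1 assessment is complete.

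**The concern.** CR by Cycle 7 Day 1 is an outcome that takes up to about 5.5 months to reach. To be counted in the CR group, a participant must stay alive, AML-free and on study until the CR marrow and, with confirmation, for about 4 weeks more. Someone who dies or leaves before then is non-CR under 6.4.1.1. Transformation is not named in that list, but Protocol 4.1 treats it as progression that ends study drug, so a participant who transforms first would not normally be counted as CR afterwards. AML before Cycle 7 Day 1 therefore falls mostly in the non-CR column, whatever CR does.

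TI has a related problem: a participant who leaves early can reach neither CR nor 56 transfusion-free days.

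The stake is interpretation. Both tables set CR beside a clinical outcome, and the AML table appears at the analysis where CR alone decides whether the study is positive (SAP 7.4.7.2). A reader could credit CR with a difference that the grouping produced.

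**Working it through.** The documents give no figure for this point and no AML, death or dropout hazards. The check asks what the tables would show if CR had no effect.

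**Inputs from the documents**
- Marrow assessments on Day 1 of Cycles 2, 4 and 7: days 29, 85 and 169 with 28-day cycles.
- CR confirmed 4 weeks (28 days) later.
- 190 participants, 2:1 (Protocol 9.4.2), about 127 and 63.
- Critical CR difference 0.1349 (SAP Table 16). With a pooled-variance z-test, p(1−p) = (0.1349/1.96)² / (1/127 + 1/63) = 0.1995, so p is about 0.275. A latent CR rate of 28% was used.

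**Assumed**
- CR first seen at days 29, 85 and 169 in 20%, 45% and 35%.
- Follow-up of 169 days plus uniform accrual over 12 to 36 months.
- Yearly hazards: AML 0.15 to 0.30, death 0.35 to 0.50, dropout 0.10.

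**Base case by formula** (AML 0.30, death 0.35, dropout 0.10, 24-month accrual)
- Total hazard 0.75; AML is the first event in 0.30/0.75 = 0.40.
- AML overall: 0.40 × [1 − e^(−0.75×0.463) × (1 − e^(−1.5))/1.5] = 0.40 × [1 − 0.707 × 0.518] = 25.4%.
- AML by day 169: 0.40 × (1 − 0.707) = 11.7% of all participants.
- Observed CR: 0.28 × [0.20e^(−0.75×57/365.25) + 0.45e^(−0.75×113/365.25) + 0.35e^(−0.75×197/365.25)] = 0.28 × 0.768 = 21.5%.
- AML in the CR group, by simulation: 20.9%. Non-CR by subtraction: (25.4 − 0.215 × 20.9)/0.785 = 26.6%. Ratio 20.9/26.6 = 0.79.
- Landmark at day 169: both groups 0.40 × (1 − 0.518) = 19.3%. Ratio 1.00.

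**Simulated range, no true CR effect.** Unless stated, hazards are as in the base case; early means before Cycle 7 Day 1.

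| Scenario | AML, CR | AML, non-CR | Crude ratio |
|---|---|---|---|
| Base case | 20.9% | 26.6% | 0.79 |
| AML 0.15 | 11.4% | 14.8% | 0.77 |
| 12-month accrual | 14.1% | 21.8% | 0.65 |
| 36-month accrual | 25.4% | 29.7% | 0.86 |
| AML 0.15, 36-month accrual | 14.1% | 16.8% | 0.84 |
| Early AML ×2 | 24.1% | 36.2% | 0.66 |
| Early death and dropout ×2 | 19.9% | 22.2% | 0.90 |
| Early AML ×0.3 | 18.7% | 18.7% | 1.00 |
| Early death and dropout ×2, AML ×0.5 | 18.2% | 17.1% | 1.06 |
| Early death and dropout ×3, AML ×0.3 | 16.5% | 12.2% | 1.35 |
| AML 0.20, death 0.50, early death and dropout ×3, AML ×0.2, 36-month accrual | 12.3% | 7.1% | 1.74 |

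With a day-169 landmark, every row returned 0.995 to 1.006. A further run under other assumed early hazards gave crude ratios of 0.67 to 1.16, and 0.98 to 1.00 at the landmark.

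**TI, no true CR effect** (assumed discontinuation hazard 0.8 to 1.2 per year, doubled early in the last case)
- Crude, CR versus non-CR: 62.4% v 53.6%, 61.2% v 49.2%, 59.1% v 40.5%; ratios 1.17 to 1.46.
- Limited to at least 56 days on treatment: 1.05 to 1.10.
- Limited to those on treatment at day 169, with no stop for lack of HI: 1.00.
- Counting only 56-day periods that start at or after Cycle 7 Day 1 fails once Protocol 7.1 is applied. A participant stopped for no HI has about 30 days of window left, and 30 < 56. With half of non-CR participants stopped this way, a null run gave 66% v 33%.

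**The case against.** Three stronger readings are tempting, and the documents support none of them.

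*That the missing landmark by itself makes CR look protective against AML.* The direction is not settled. Early deaths and dropouts also land in the non-CR group, before AML can be counted, and this pushes the ratio up. The reversal should not be overstated either: the Schedule of Activities collects transformation in Disease and Survival Follow-up, so stopping treatment does not by itself end ascertainment.

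*That these tables are the plan's evidence that CR brings clinical benefit.* No section says so. Protocol 4.2 justifies CR from cited literature and earlier approvals. SAP 7.4.5.7 presents the AML count as a summary to cover the wait for EFS. The TI table does aim at association, but it is labelled exploratory. Neither carries a test or touches alpha, stopping, the CR test or the OS test.

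*That a landmark with later TI periods would also repair 7.4.6.10.* It would not, because of the no-HI stop and the 30-day window. Part of the CR-TI link is also definitional: CR needs hemoglobin and platelet thresholds, with counts free of transfusion for 7 days. No landmark removes that part.

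What stands against the objection is that a descriptive split whose null ratio can lie anywhere from about 0.65 to 1.74 cannot be read, and for AML the remedy is simple.

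**Conclusion.** The point holds as a minor one. The AML split in SAP 7.4.5.7 groups participants by a post-randomization response without an at-risk condition, and can show a CR difference when none exists. The null ratio is about 0.65 to 0.86 with constant hazards or front-loaded AML, 0.90 with early death and dropout doubled, and 1.0 to 1.7 when early AML is rarer, with or without more early death and dropout. These figures rest on assumed hazards, CR timing and accrual. The return to about 1.00 at a Cycle 7 Day 1 landmark did not depend on which of these sets was used.

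The TI table has a similar at-risk problem, with a null ratio of 1.17 to 1.46 under the assumptions used, but it needs a different remedy.

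**What to change.** **SAP 7.4.5.7.** In the split by CR status:
- Include only participants known to be alive and AML-free at Cycle 7 Day 1. For those who stopped treatment earlier and have no such visit, name a nominal date, for example study day 169.
- Classify CR by the status at that date. State how a CR first seen on the Cycle 7 Day 1 marrow is handled, since count recovery may follow by up to 2 weeks (Protocol 8.1.1) and confirmation comes 4 weeks later.
- Count AML only after that date, and report earlier AML by treatment arm only.

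**SAP 7.4.6.10.** Limit the table to participants still on treatment at Cycle 7 Day 1, with response categories as reached by then, and count TI from randomization up to that date. Everyone then has the same nominal window of 168 days, and the stop for lack of HI comes after it. Do not require the 56-day period to start at or after Cycle 7 Day 1. State that the table is descriptive and that part of the CR-TI link follows from the definition of CR.

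**Cost.** A few SAP sentences and changes to two table programs. The AML split will hold fewer events, and TI reached after Cycle 7 Day 1 drops out of this table; it stays in the analyses of 7.4.5.1 and 7.4.6.7. Alpha, sample size and conduct are unchanged.
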